## Overview of the Overall Study Approach

The content of subsequent sections warrants an introduction to the overall approach to the research involved. The research as a whole involves two separate but related components: (1) **a VA component** involving all VA recruitment, VA data collection, and all processes involving VA data (addressed by the current VA IRB application and referred to as the “VA component”), and (2) **a non-VA component** involving non-VA data collection that occurs entirely outside the VA and does not involve any VA data. This means that the current human subjects application and the VA informed consent processes described in this application pertain only to the VA component of the research (the VA research processes). Separate from the VA component of the research is the non-VA component, which will be carried out by researchers at the University of Washington (UW). Participants in the VA component of this research will be provided information that they can use to initiate contact, screening, and possible enrolment in the non-VA component conducted by UW researchers. The non-VA component of the research will run in parallel with the VA research processes, yet involves non-VA data collection only. The UW research processes will undergo a separate process of IRB approval at UW, including a separate process of informed consent. This non-VA data collection will include all e-Questionnaires described above, administered by a private (non-VA) data collection company specializing in secure HIPAA-compliant and 21 CFR 11-compliant electronic questionnaire administration (DatStat). DatStat has a successful track record for conducting secure electronic questionnaire administration for another current UW research study. Acquisition of e-Questionnaire data in this proposed manner- in partnership with UW researchers- permits the ability to conduct frequent serial assessments with quasi-randomized timings via e-Questionnaires, since at the current time there exist no feasible processes to collect such data as VA data using VA devices. At interim time points during the VA component of this study, e-Questionnaire data being collected by UW researchers as part of the non-VA component of this study will be downloaded by VA research study staff involved with this VA research study, at which time such data will become VA data and will not subsequently be shared outside the VA during the study. **In summary, no VA data produced as part of this VA research study will be shared outside of the VA at any point during the conduct of this VA research. However, non-VA data collected by researchers at the UW will be shared with this VA research team.** Thus, the flow of research data in this VA research study is only into the VA, and never out of the VA.

**Most aspects of the proposed research as described in this human subjects research application pertain to the “VA component” of the study (VA data collection and VA research processes).** However, in order to provide a complete picture of what the study entails for reviewers of this

protocol/application, the protocol also provides information about aspects of data collection occurring as part of the non-VA (UW) component of the study. From this point on in the protocol, **data collection or study processes relevant only to the non-VA (UW) component of the study are provided in blue font such as this, to emphasize aspects that are not covered by the VA human subjects review processes (i.e. by the VAPSHCS IRB)**, but will be covered by the UW human subjects review processes (i.e. **by the UW IRB**). In addition, **communications with the IRB Director, Information Systems Security Officer, and Privacy Officer resulted in the recommendation during the initial IRB approval process that we provide to potential VA participants a “Summary of UW Research” processes (Attachment S) to ensure that participants are fully aware from the outset about all aspects of being a study participant, including both VA and non-VA components of the research. Attachment S was previously approved with the original IRB submission, and a revised version is submitted with PRAF 1**. As appropriate in the future, we will submit to the VAPSHCS IRB any documentation pertinent to study processes at UW and relevant documentation from the UW IRB.

## 5.1 Study Design

This will be an ***observational***, longitudinal case-crossover study nested within a cohort study, following up to 730 Veterans seen for LBP in VA primary care prospectively for 12 months. Study procedures will not make changes to nor in any way affect the typical medical care for LBP provided at VAPSHCS. **All study assessments following recruitment will be “e-Questionnaires” that participants complete using their own personal electronic devices (smartphones, tablets, or PCs, not provided by the study).** There are two types of e-Questionnaires that participants will complete: “*scheduled e-Questionnaires*” and “*flare window e-Questionnaires*”. Scheduled e-Questionnaires are quasi-random, ‘cue-elicited’ frequent assessments that will be repeated numerous times throughout the 1-year follow-up period. Cues to complete scheduled e-Questionnaires are automated “e-Alert” notifications sent by text message and email at the start of each “*scheduled assessment window*”, the 3-hour period during which a scheduled e-Questionnaire may be completed. ***Scheduled e-Questionnaires will occur three times each week during weeks 1-4 of follow-up, once a week during weeks 5-8, and twice a month during months 2-12.*** Participants will also complete unscheduled “*flare window e-Questionnaires*” on an *ad hoc* basis, if they experience new flares of LBP at any time during the 1-year follow-up period. At study entry, participants will receive training on how to complete flare window e-Questionnaires, if they experience flares of pain, by logging on to a secure Participant Portal (the **Flares of LBP with Activity Research Study** or “FLARES” website) within 3 hours after the onset of a new pain flare. In addition, all scheduled e-Questionnaires will remind participants to complete a flare window e-Questionnaire if they have a new pain flare. Scheduled e-Questionnaires and flare window e-Questionnaires generally contain the same question items, however, scheduled e-Questionnaires inquire about activity exposures *preceding the start of the scheduled assessment window* (when e-Alert notifications are sent), and flare window e-Questionnaires inquire about activity exposures *over the time period preceding the flare onset*. Each e-Questionnaire will begin by prompting the participant with the definition of a LBP flare. Participants will then report whether or not they are experiencing a flare, the primary outcome for Aim 1 of this study. E-Questionnaires will also inquire about activity exposures that have occurred over the 24-hour period prior to the assessment window start and - *if* an activity is reported – ask for further clarification of whether the activity was performed in the 2-hour period prior to the assessment window start. Further questions included in every e-Questionnaire are time-varying pain and psychological covariates (pain intensity, depression, catastrophizing, stress, etc.) assessed using brief, validated measures. All e-Questionnaires are inherently time lagged for activity-flare relationships, since they capture *current* flare status at time=t, and activities in the 24-hour period *before* the start of the assessment window/flare onset (t-1). Participants may also be offered to wear the optional ActiGraph wGT3X-BT unit continuously for weeks 1-4 of the study. Due to the participant burden involved with frequent serial e-Questionnaire assessments, a run-in period during weeks 1 and 2 of follow-up will exclude those individuals unable to maintain compliance with these assessments. Aim 1 analyses will examine the short-term effects of 10 specific activity categories on participant-reported flares across all study assessments over 1-year follow-up. Aim 2 analyses will examine associations between the frequency of exposure to 10 specific activity categories over weeks 1-4 of follow-up, and long-term functional recovery at 12 months as defined by the RMDQ. All analyses will use a biopsychosocial framework accounting for potential confounders (sociodemographics, psychological factors, etc.) and effect modifiers, and will include sensitivity analyses to examine the robustness of findings and important study assumptions.

Please see “Overview of the Overall Study Approach” subsection in 3.0 above. As mentioned, the study as a whole involves two separate components: (1) a VA component involving all VA recruitment, VA data collection, and all processes involving VA data (addressed by the current VA IRB application and referred

to as the “VA component”), and (2) a non-VA component involving non-VA data collection that occurs entirely outside the VA and does not involve any VA data. Non-VA data collection involves e-Questionnaires (referred to as “e-Surveys” in participant-facing materials). e-Questionnaires are to be administered as part of the non-VA (UW) research processes and are therefore provided to the VA IRB for completeness, but not for VA review. E-questionnaires are labelled as Attachments Q1-Q3.

ActiGraph units will not be available for participant use by the time when recruitment could otherwise be started. ActiGraph-related research questions are separate from the primary study aims which rely on participant-reported data, and are therefore non-essential and optional for participant use. Participants may or may not be offered to wear an ActiGraph and use of this device is optional. Due to the expected unavailability of ActiGraph units at the time when recruitment is started, potential participants approached at times when Actigraphs are not available will be offered the opportunity to participate without wearing the ActiGraph. With the current version of the protocol, we provide a revised Information Statement document that describes participation in the study either with or without participation in that component of the study that involves the ActiGraph. In other words, the revised Information Statement is now applicable whether or not the participant wears the ActiGraph as part of their study participation.

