**5.6.2 a. Aim 1 analyses:** We will examine associations between activity group exposures and the participant-reported flares outcome in conditional logistic regression models, using data from all scheduled and flare window e-Questionnaires over 1- year. There will be one model for each of the 10 primary activity categories. Models will include activity categories as time-varying predictors as in **equation 1**, where  $Y$  is the outcome (flare vs. no flare),  $x$  is the activity

exposure (yes vs. no), and  $C$  represents potential time-varying confounders (psychological factors, other activities). The letter  $i$  indicates the  $i^{\text{th}}$  individual ( $i = 1, 2, \dots, n$ ),  $j$  indicates the  $j^{\text{th}}$  time of follow-up ( $j = 1, 2, \dots, n_i$ ) and  $x_{i(j-1)}$  indicates an activity that was performed in the exposure window prior to the  $j^{\text{th}}$  time (either the start of the control window [scheduled e-Questionnaire] or time of flare onset [flare window e-Questionnaire]). As previously noted, the survey methods are such that activity exposure and flare outcome are inherently time-lagged, with exposure preceding outcome.  $\beta_w$  represents the association of activity  $x$  with flare outcome  $Y$  within individuals (the ‘within-individual effect’), or the expected odds of a flare with change in the activity exposure for a given individual. These analyses will yield odds ratios (OR) and 95% confidence intervals for within-individual ‘effects’ of activity triggers on an LBP flare. The initial analytic approach (**Figure 3**) will examine the association between binary activity exposure and binary flare outcome, with explicit adjustment for pain NRS and number of prior flares measured at time= $j-1$ , and time-variant confounders selected based on conceptual importance; *by design*, the case-crossover method uses each person as their own control, accounting for known and unknown confounds that are fixed or relatively stable over time (i.e., age, sex, sociodemographics, medical and LBP history, work-related factors, and underlying psychological predispositions). We will use a Bonferroni-corrected threshold of  $p=0.005$  for each

$$\log \left[ \frac{Pr(Y_{ij} = 1)}{1 - Pr(Y_{ij} = 1)} \right] = \beta_{0i} + \beta_w x_{i(j-1)} + \gamma C_{i(j-1)}, i = 1, 2, \dots, n; j = 1, 2, \dots, n_i \quad (1)$$

[figure not shown]

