\*Analysis includes all scheduled and flare window e-Surveys. Activity exposures over prior 24-hr and 2-hr effect periods, and current flare status, are inherently time-lagged.

primary activity-

flare comparison to account for 10 statistical comparisons (one for each of the 10 activity categories). We will further examine for activity-flare associations after accounting for important relationships based on theory and clinical knowledge, including the following: dose-response relationships; work- specific activity-flare associations; multivariate analyses including other potential confounders (other time-varying activities, depression, PTSD, stress, catastrophizing); potential moderators; different effect-periods of activity exposures (i.e., 24 vs. 2 hours); possible biases (e.g., conscious activity avoidance and carry-over effects); and clinical subgroup analyses (lumbosacral radicular syndrome [LSRS] symptomatic lumbar spinal stenosis [SLSS] diagnosed by a specialist, ascertained by chart review). We will also conduct similar subgroup analyses as secondary analyses, targeting the expanded target population subgroups described above (facet-mediated pain, SIJ-mediated pain, spondylolysis, ascertained by EHR review). We will analyze the reliability and accuracy of these subgroups. Of note, the primary analysis of walking, standing, and sitting will use the ActiGraph data (which are only obtained for the 1st 4 weeks of follow-up); secondary analyses will use the self- reported data for these 3 groups over the entire 1-year follow-up, and will also examine the association between ActiGraph and self-reported data. After these analyses using the binary flare outcome, we will use an analogous approach to examine relationships between activity categories and the secondary (continuous) outcome of NRS LBP intensity, with linear mixed-effects regression. These analyses account for potential biases that might be introduced by participant self-identification of flare status; if no such bias exists, we would expect the direction of effects to be similar to those obtained in the initial analysis of flares.

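### Aim 1 has no visible rule for a flare already under way at a scheduled e-Questionnaire; if it counts as a case, its activity window runs past onset and the odds ratio is biased

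*Combined protocol and SAP*

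**What the plan says.** The aim in section 3.0 is to find activities that trigger flares, so the target is onset. The recorded outcome in section 5.1 is flare status at the time of answering, on every form: "Participants will then report whether or not they are experiencing a flare, the primary outcome for Aim 1 of this study".

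The two forms anchor exposure differently. For scheduled forms, "E-Questionnaires will also inquire about activity exposures that have occurred over the 24-hour period prior to the assessment window start". Flare-window forms are completed by participants "if they experience new flares of LBP at any time during the 1-year follow-up period" and ask about the time before onset. Section 5.1 nevertheless states that "All e-Questionnaires are inherently time lagged for activity-flare relationships".

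Section 5.6.2a fits conditional logistic regression "using data from all scheduled and flare window e-Questionnaires". The footnote there repeats both parts: "Analysis includes all scheduled and flare window e-Surveys", and "Activity exposures over prior 24-hr and 2-hr effect periods, and current flare status, are inherently time-lagged". One phrase points elsewhere. The time index of the exposure is "either the start of the control window [scheduled e-Questionnaire] or time of flare onset [flare window e-Questionnaire", which reads as if scheduled records supply controls and flare-window records supply cases.

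Section 5.6.1 bases the Aim 1 power on scheduled e-Questionnaires alone and assumes nothing from flare-window forms. No visible text says what happens to a scheduled record completed during a continuing flare, or how a flare reported on both forms is counted.

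**The concern.** Suppose a flare starts, and the next alert arrives a day and a half later. The participant reports being in a flare, and the form asks about the 24 hours before the alert. All of that window lies after onset. The record enters the model as a case, but what it measures is behaviour during a flare, so the claim that exposure precedes outcome is false for it. Only a flare that begins between the alert and the answer, at most 3 hours later, keeps a clean window.

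If activity does not change during flares, the post-onset time dilutes a real trigger and the OR moves towards 1. If people cut back, the OR falls further and an activity with no effect can look protective. If activity rises, a null activity can look harmful. Section 5.6.1 regards ORs of 1.5 to 2.0 as meaningful, and 5.6.3 turns the estimates into tables meant to inform activity advice, so a fall from 1.5 to about 1.2 would matter.

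**Working it through.** **The plan's own figures.** Alpha: 0.05/10 = 0.005. Sample size: 440/(1 - 0.40) = 733, against 730; 290/730 = 39.7%. The stated power cannot be derived exactly because flare frequency is not given. With 440 people, 29 completed scheduled records each and an assumed flare frequency of 6%, simulation gives 89%, 75% and 81% for the three scenarios stated as about 90%, 80% and 80%. Every case in that calculation is a scheduled flare; without them it has no cases.

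**Inputs.** From the documents: 36 scheduled records (5.2.7), the 24-hour window and an answer within 3 hours (5.1). Assumed: true onset OR 1.5; activity in 15% of 24-hour windows; one onset per 30 flare-free days; half of onsets logged on a flare-window form; fixed flare length; activity rate multiplied by r during a flare.

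**Hand calculation, 3-day flares.**
- Case records per person: flare-window 0.5 x 365/33 = 5.53; scheduled 36 x 3/33 = 3.27; total 8.80.
- Scheduled flares that begin after the alert: mean delay 1.5 h/72 h = 2%. Share of all case records with a window running past onset: 3.27 x 0.98/8.80 = 36%.
- Control odds: 0.15/0.85 = 0.1765. Let L = -ln(0.85) = 0.1625.
- Exposure at onset: 1.5 x 0.15/(0.85 + 1.5 x 0.15) = 0.225/1.075 = 0.2093.
- Scheduled case: time since onset is uniform over 72 h, so 2/3 of windows lie wholly after onset and 1/3 partly.
- Wholly after: 1 - exp(-rL) = 0.1500 (r = 1) or 0.0780 (r = 0.5).
- Partly after: 1 minus the mean, over u from 0 to 1, of [0.85 + 1.5(exp(-L(1-u)) - 0.85)]/1.075 x exp(-rLu) = 0.1788 or 0.1441.
- Scheduled average: (2/3)(0.1500) + (1/3)(0.1788) = 0.160 (unchanged); (2/3)(0.0780) + (1/3)(0.1441) = 0.100 (halved).
- Pooled: 0.36 x 0.160 + 0.64 x 0.2093 = 0.191, odds 0.237, **OR 1.34**; halved 0.170, odds 0.205, **OR 1.16**.
- Null activity, halved: partly-after value 0.1145, scheduled average 0.090, pooled 0.36 x 0.090 + 0.64 x 0.15 = 0.128, **OR about 0.83**.

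**Hourly simulation of the all-records model** (30,000 people, 365 days, exact conditional fit; simulation error about 0.02):

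| Flare length | 1 day | 2 days | 3 days | 5 days |
|---|---|---|---|---|
| True 1.5, activity unchanged | 1.48 | 1.38 | 1.35 | 1.27 |
| True 1.5, activity halved | 1.44 | 1.26 | 1.17 | 1.02 |
| Null, activity halved | 0.97 | 0.88 | 0.84 | 0.76 |
| Null, activity raised by half | 1.05 | 1.09 | 1.16 | 1.22 |
| Case windows past onset | 16% | 27% | 36% | 48% |

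A separately coded simulation gives 1.47 and 1.42 (unchanged, halved) at 1 day, 1.39 and 1.19 at 3 days, and 0.82 for the halved null at 3 days. Cases anchored at onset return 1.48-1.53 in the first and 1.50-1.57 in the second.

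**Sensitivity at 3 days (unchanged; halved).** With 25% of onsets logged: 1.27; 1.01. With 100%: 1.40; 1.29. With activity at 5%: 1.35; 1.18. At 25%: 1.35; 1.15.

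**Does the planned adjustment repair it?** Section 5.6.2a adjusts for pain NRS and number of prior flares at j-1, which can mean the exposure window or the previous questionnaire. At 3 days, halved (assumed NRS mean 3, or 6 in a flare, SD 1.5), the unadjusted OR is 1.19. It is 1.19 with the previous-questionnaire NRS and flare count, and 1.22 with NRS 24 h earlier and flare count. Flare status 24 h earlier, which is not in the plan, would give 1.37.

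**If scheduled flares are controls instead:** the OR is 1.47-1.59 for a true 1.5, so bias is small, but the simulation in 5.6.1 does not describe that analysis.

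**The case against.** The strongest reply is that the deciding material is not visible. Figure 3 and the questionnaire attachments are not shown; the forms may record onset time or separate new from continuing flares, and the control-window wording may mean that scheduled flares are never cases. This stands against saying flatly that ongoing flares become cases. It does not remove the point: the visible analysis text uses no onset item, and the control reading contradicts 5.6.1.

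Section 5.6.1 also calls flares transient. If they last about a day, pooled bias is small (1.42-1.48 for a true 1.5). That stands too. Section 5.1 further has every scheduled form remind participants to file a flare-window form, which could push logging above the assumed half, though at 100% logging the 3-day OR is still 1.40 or 1.29.

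Section 5.6.2a lists activity avoidance and carry-over among biases to examine, and plans an NRS analysis. Neither answers the timing problem: the first has no stated method and leaves the primary model unchanged, and the second addresses self-identification of flares.

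Finally, anchoring on onset rests the primary result almost wholly on self-initiated reports. The plan already worries about over-reporting (5.2.7) and self-identification (5.6.2a). Selective logging and recall are not quantified here, and this is a real cost.

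**Conclusion.** The point holds in conditional form and is a should-fix. The visible sections disagree on whether a scheduled flare is a case. If it is, records from continuing flares break the stated ordering of exposure and outcome, and one flare can be counted twice. For a true OR of 1.5 the planned model would give about 1.42-1.48 with 1-day flares, and with 3-day flares 1.35-1.39 (activity unchanged) or 1.17-1.19 (halved). A null activity halved during 3-day flares would give 0.82-0.84. Flare length, activity change, onset rate and logging share are all assumptions. The simulation covers a year of self-report, so it does not represent walking, standing and sitting, whose primary analysis uses 4 weeks of ActiGraph data.

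Two stronger readings are not supported. A reader might apply the results for scheduled cases alone (for a true 1.5: 1.26 to 1.05 over 1 to 5 days with activity unchanged, 1.01 to 0.58 halved) to the trial's estimates. Those concern only the basis of the power calculation; the planned model pools both forms. A reader might also infer that triggers will be masked or look protective. Section 5.6.2b expects activity restriction early in an LBP episode, which would fit downward bias if it also held in flares. The documents do not say that it does, and raised activity biases the other way.

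**What to change.** In 5.6.2a:
- Reconcile the control-window wording with 5.6.1 and state whether a flare on a scheduled form can be a case.
- Define a case as a new flare whose exposure window ends at or before onset: flare-window records, plus scheduled reports only where onset is known to follow the exposure window.
- Treat scheduled records during a continuing flare as neither case nor control, and count each flare once.
- Say what j-1 means for NRS and prior flares, and anchor ActiGraph windows in the same way.
- Report the all-records current-flare model alongside as a sensitivity analysis.
- Restate the power in 5.6.1 for the chosen case definition.

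The cost is SAP wording, a rerun simulation and at most one onset-time item. For data without onset times, use flare-window cases against flare-free scheduled controls. Scheduled reports would add few cases: 1.5 h over the flare length gives about 6%, 3%, 2% and 1% of scheduled flares starting after the alert at 1, 2, 3 and 5 days. With 3-day flares and half of onsets logged, cases per person fall from 8.8 to 5.6 and the SE of ln OR at n = 440 rises from 0.048 to 0.056. With a quarter logged, cases fall from 6.0 to 2.8 and the SE rises from 0.057 to 0.075. The heavier reliance on self-initiated reports should be checked against the retained all-records model and the NRS outcome.
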